#### 3. Investigational Plan

#### 3.1. Overall Study Design and Plan

Subjects will dose for up to 12 weeks (84 days) with NVN1000 Gel or Vehicle Gel coadministered with an equal volume of a carboxymethyl cellulose hydrogel. Subjects will be randomized 3:1 to active:vehicle in 4 dose cohorts initiated at NVN1000 8% Gel. The safety/tolerability of each cohort will be assessed by an independent data safety monitoring board (DSMB) after the first 12 subjects of each cohort complete 2 weeks of dosing.

Figure 3–1 depicts the overall study design for this 12 week, variable dose, randomized, double blind study in subjects with EGW/PAW dosed with NVN1000 Gel or Vehicle Gel. Subjects receiving current treatment for EGW/PAW may enter a wash out period after screening of up to 35 days prior to randomization.

Subjects who are found to be cleared of all warts at a visit will discontinue treatment at that time. If warts recur at a subsequent visit prior to end of treatment, subjects will be dispensed a new kit of the same treatment they previously received.

		Vehicle Gel	to match cohort	dosing	
			el 8% twice dai	ly (Cohort 1)	
	Randomization: 3:1	- NVN1000 C	el 8% once dail	y (Cohort 2)	
	active.venicle	- NVN1000 C	el 16% once dai	ily (Cohort 3)	
		- NVN1000 C	el 24% once dai	ily (Cohort 4)	
Visits		T T' '. 1			
Screening	Baseline	Visit I	Visit 2	Visit 3	Visit 4/ET
Day -35 to Day -1	Day 0	Day 14	Day 28	Day 56	Day 84
	Study Week	2	4	8	12

Figure 3–1: Study Diagram

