#### 4. General Statistical Considerations

All statistical processing will be performed using SAS® version 9.2 or higher unless otherwise stated. Statistical significance will be based on two-tailed tests of the null hypothesis resulting in p-values of  $\leq 0.05$  unless stated otherwise. Inferential testing will compare each active treatment group to the vehicle treatment group. Comparisons will not be performed between active treatments. All p-values will be reported without concern for controlling for multiplicity. Efficacy analyses will be performed for the intent-to-treat (ITT) and per-protocol (PP) populations. Safety analyses will be performed using the safety population as defined in section 4.3.2

Continuous data will be summarized with sample size (N), mean, median, standard

deviation, minimum and maximum. Categorical data will be summarized with number of subjects N, frequency counts, and percentages.

For analysis, baseline warts are defined as warts that are present at the baseline visit. Total warts include all warts present, even if they were not present at the baseline visit. Complete clearance is defined as zero warts present. Partial clearance is defined as a reduction in number of warts from baseline.

The last evaluation for each endpoint prior to the first dose of study drug will be used as baseline for all analyses.

For safety analyses including tolerability, summaries will be performed by treatment arm as well as "Pooled Active", which is a total of all NVN1000 treatment arms.

For disposition, demographics, efficacy, compliance and tolerability analyses, Vehicle Gel subjects will be summarized separately by dosing frequency (QD and BID). For other safety analyses, vehicle subjects will be combined. Subjects will be listed by actual treatment, with vehicle subjects listed separately by dosing frequency.

For subjects who are taken off treatment due to complete clearance of warts and then later restart treatment due to recurrent warts, the date of last dose for analysis purposes will be the date of last dose for the second treatment interval.

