## 7.2.1. Exposure and Compliance

Duration of exposure will be calculated in days as date of last dose of study medication– date of first dose of study medication+ 1. Percent compliance will be calculated as the number of total doses received divided by the number of planned doses times 100. The number of planned doses will be calculated as follows:

2 times the duration (days) of exposure - 1 for cohorts dosing twice daily,

and

1 time the duration (days) of exposure for cohorts dosing once daily,

The number of doses received will be calculated as the number of planned doses minus the total number of missed doses as indicated in the subject diaries. Descriptive statistics including the number of subjects, mean, standard deviation, median, minimum, and maximum for duration of study exposure and percent compliance will be provided by treatment group using the safety population. Vehicle Gel subjects will be separated into QD and BID groups for both exposure and compliance summaries. Compliance and treatment duration will also be listed by subject.

In addition, number of missed doses for each subject based on subject diaries will be summarized in a frequency table and listed by subject. Doses missed specifically for tolerability reasons will likewise be summarized in a frequency table and listed by subject.

For subjects who experience complete clearance, the number of missed doses and compliance will only be calculated up to and including the date of the first visit where the subject had a total wart count of 0. Any subsequent dosing due to recurrent warts will not be considered for analysis of missed doses or compliance.

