#### 8. Efficacy Analysis

Efficacy data is collected at each study visit. Wart count data including derived primary and secondary endpoint data such as complete clearance, time to complete clearance, time to recurrence, etc. will be presented in listings by subject. Subjects may receive more than one course of treatment if they experience complete clearing and subsequent recurrence of warts. Assessment of time to clearing, time to recurrence, and clearing at or before Week 12 will be assessed based on the initial treatment course (i.e., first instance of clearing/recurrence only.) For efficacy assessments by visit (i.e., at Weeks 2, 4, 8 and 12), data will be summarized without regard to treatment course. (e.g., assessments at Week 8 may include data for subjects still on their initial treatment course as they have not yet achieved clearance, subjects off treatment as they have previously cleared but not yet experienced a recurrence, and subjects on a second course of treatment after prior clearance and recurrence.)

Wart count data including derived primary and secondary endpoint data such as complete clearance, time to complete clearance, time to recurrence, etc. will be presented in data listings by subject.

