## 9. Safety Analysis

#### 9.1. Adverse Events

All AEs that occur during the study will be recorded and classified on the basis of Medical Dictionary for Regulatory Activities (MedDRA) terminology. Treatment-emergent AEs (TEAEs) are defined as AEs with an onset on or after the date of the first study drug dose, and occur within 30 days of the last study drug dose. Adverse events noted prior to the first study drug administration that worsen after baseline will also be reported as TEAEs and included in the summaries.

All information pertaining to an AE noted during the study will be listed by subject, detailing verbatim term given by the principal investigator or designee, preferred term, system organ class (SOC), onset date, resolution date, severity, seriousness, action taken, outcome, and drug relatedness. The event onset will also be shown relative to study drug initiation (in number of days). Listings will be provided for all TEAEs, adverse events prior to date of first treatment, and adverse events starting more than 30 days after last study drug use.

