#### **10. Interim Analysis**

There will be 4 Data Safety Monitoring Board (DSMB) meetings during the conduct of this study to evaluate safety and tolerability prior to dose modification. A subset of the final safety and tolerability tables and listings, will be provided to the DSMB for review. Outputs to be provided to the DSMB are documented in the DSMB charter. No inferential statistics or hypothesis testing is planned for the DSMB analyses. DSMB analyses will be unblinded to actual treatment. The analyses for the DSMB will be performed by a separate, independent statistics team.

In addition, an Interim Analysis including efficacy summaries will be conducted upon completion of Cohorts 1 and 2 to assist in the planning of future trials. No stopping rules for futility or early efficacy assessment will be applied as part of the interim analysis. The analysis will only be conducted on the subjects in cohorts 1 and 2, and a subset of tables from the primary analysis will be presented. Pairwise comparisons will be done between each active treatment in the cohorts and Vehicle Gel and nominal p-values will be presented without adjustment. Additionally, no adjustments will be made to p-values in the final analysis as a result of the interim analysis.

The analysis set for the interim analysis will be subjects randomized into one of the first two cohorts. All subjects randomized on or prior to the last randomization date entered into IVRS for Cohort 2 will be included.

Table	Population
Table 14.1-1 Subject Disposition	All Randomized Subjects

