#### Table 2: Interim Analysis Outputs

Table 14.1-2 Demographics and Baseline Characteristics	Intent-to-Treat Population		
Table 14.2-1.1 Complete Clearance of Baseline EGW/PAW at	Intent-to-Treat Population		
or Before Week 12			
Table 14.2-1.3 Complete Clearance of Baseline EGW/PAW at	Intent-to-Treat Population		
or Before Week 12 by Gender			
Table 14.2-7.1 Percent Change in Baseline EGW/PAW at	Intent-to-Treat Population		
Weeks 2, 4, 8, and 12			
Table 14.2-9.1 Count of Total Warts at Weeks 2, 4, 8, and 12	Intent-to-Treat Population		
Table 14.3-1 Study Drug Exposure (Days) and Missed Doses	Safety Population		
Table 14.3-3.1 Summary of Tolerability Evaluations	Safety Population		
Table 14.3.1-2 Treatment-Emergent Adverse Events by System	Safety Population		
Organ Class and Preferred Term	_		

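### For subjects who clear, stop drug and restart, the SAP counts the off-drug gap as exposure: 84 days reported for 70, 56 or 42 on drug

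*SAP*

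**What the plan says.** SAP 3.1 stops treatment at the visit where a subject is found clear of all warts. If warts recur at a later visit before the end of treatment, "subjects will be dispensed a new kit of the same treatment they previously received".

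For such a subject, SAP 4 states that "the date of last dose for analysis purposes will be the date of last dose for the second treatment interval".

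SAP 7.2.1 then sets the measure: "Duration of exposure will be calculated in days as date of last dose of study medication", minus the date of first dose, plus 1. The formula has no term for an interruption.

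The last paragraph of SAP 7.2.1 does deal with restarts, but only for adherence. Missed doses and compliance are cut at the first visit with a total wart count of zero, and "Any subsequent dosing due to recurrent warts will not be considered for analysis of missed doses or compliance". Duration of exposure is not named there.

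SAP 8, describing who contributes to by-visit efficacy data, lists "subjects off treatment as they have previously cleared but not yet experienced a recurrence" as a separate group.

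The result appears in "Table 14.3-1 Study Drug Exposure (Days) and Missed Doses", which SAP Table 2 also lists as an interim output. SAP 10 says that the interim analysis is done "to assist in the planning of future trials".

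**The concern.** Read together, SAP 3.1, 4 and 7.2.1 count as exposure a period in which the subject has been told to stop the drug and which SAP 8 itself describes as off treatment. The interruption is part of the design and can last weeks; it is not an occasional missed dose.

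Two consequences follow for a restarted subject:

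- The figure under an exposure heading is not days on drug, and the table title gives no sign of this.
- The same table pairs it with a missed-dose count on another time base. Exposure covers both courses and the gap, while missed doses cover the first course only.

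The error is also not random. It arises only in subjects who cleared and then recurred, so its frequency depends on response and may differ between arms. A reader who uses Table 14.3-1 to judge how much drug subjects received, or to plan a later trial from the interim output, would be given too many days for these subjects.

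**Working it through.** **Inputs**

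- Visit days 14, 28, 56 and 84, with windows of ±3 days at Week 2 and ±5 days afterwards (Protocol Table 4; SAP 11.1).
- Planned maximum treatment of 84 days (SAP 3.1).
- Exposure = last dose date − first dose date + 1 (SAP 7.2.1), with the last dose taken from the second course (SAP 4).
- Drug stops at the clearance visit *c* and restarts at the recurrence visit *r* (SAP 3.1).

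**Day-count assumption.** The first dose is on Day 0, and each course's last dose falls on the day before the visit that ends it.

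**Plan's own figure.** A subject dosed continuously has a last dose on Day 83: 83 − 0 + 1 = 84 days, which matches the planned 84.

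**Restarted subjects at scheduled visits, dosing to Week 12.** Reported exposure is 84 in every case. Days on drug = 84 − (*r* − *c*).

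| Clear | Restart | Gap | Reported | On drug | Ratio |
|---|---|---|---|---|---|
| Day 14 | Day 28 | 14 | 84 | 84 − 14 = 70 | 1.20 |
| Day 28 | Day 56 | 28 | 84 | 84 − 28 = 56 | 1.50 |
| Day 14 | Day 56 | 42 | 84 | 84 − 42 = 42 | 2.00 |

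These are the only three clear/restart patterns at scheduled visits, because a recurrence first seen at Week 12 leads to no further dosing. Only subjects who clear by Week 4 and recur by Week 8 can be affected.

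**Other day convention.** If doses are also taken on the visit days, the figures become 85 reported against 72, 58 or 44 on drug, with ratios of 1.18, 1.47 and 1.93.

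**Visit windows.** The windows are Days 11–17, 23–33, 51–61 and 79–89. Ratio = end day ÷ (end day − gap).

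| Pattern | Gap (days) | Smallest ratio | Largest ratio |
|---|---|---|---|
| Week 2 to Week 4 | 6–22 | 89/83 = 1.07 | 79/57 = 1.39 |
| Week 4 to Week 8 | 18–38 | 89/71 = 1.25 | 79/41 = 1.93 |
| Week 2 to Week 8 | 34–50 | 89/55 = 1.62 | 79/29 = 2.72 |

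**Second course ending early.** Clear at Week 2, restart at Week 4, clear again at Week 8: 56 reported against 14 + 28 = 42 on drug (1.33). As an illustration, clear at Week 2, restart at Week 8, stop seven days later: 63 reported against 14 + 7 = 21 on drug (3.0).

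**What does not move.** Compliance is cut at first clearance, so per-protocol membership through the 80–120% rule is not affected by the gap. Adverse event percentages use numbers of subjects as the denominator (SAP 9.1.2 to 9.1.4). No test uses exposure.

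**The case against.** The strongest reply is that this is a declared convention. First-to-last-dose duration is common, SAP 7.2.1 states the formula, and SAP 4 addresses the restarted subject directly. The different treatment of missed doses also has a sound purpose: without the cut, doses not taken while off drug as instructed could count against compliance. On this view only the label is at issue. That supports a low grade, but it does not make the number right. The gap is planned, can last 14 to 42 days at scheduled visits, and is reported under a title that reads as days of exposure.

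Other points have some weight:

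- **Few subjects.** A restart needs clearance of all warts by Week 4 and recurrence by Week 8, so the ratios are per affected subject and say nothing about arm means. The 2.72 needs three visits at opposing window edges, and the 3.0 needs a supposed early stop. This stands.
- **Restart is not in the protocol.** Protocol 4.2.1 keeps a fully cleared subject in follow-up and gives no instruction to treat again. This makes the number affected less certain, but the SAP plans for restarts and needs a correct rule for them.
- **Approximate recovery.** Wart counts, clearance and treatment duration are listed by subject, so a reader could roughly reconstruct the gap. The summary table would still be wrong.
- **Thin interim link.** The table is one of several interim outputs and covers Cohorts 1 and 2 only; nothing says exposure days will drive planning. This is fair, and the point does not depend on it.

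**Conclusion.** The concern holds, at minor severity. For a subject who clears, stops and restarts, the SAP reports the span from first to last dose as exposure. At scheduled visits with dosing to Week 12, that is 1.2, 1.5 or 2.0 times the days on drug, and 1.07 to 2.72 times across the allowed visit windows. The exact day counts rest on each course ending the day before a visit; the alternative convention changes them only slightly.

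The damage is limited to the exposure summary and the by-subject listing. The effect on arm means is probably small, but it cannot be computed: the documents give no clearance or recurrence rate for this drug and no fixed cohort size.

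**What to change.** In SAP 7.2.1, define duration of exposure for restarted subjects as the sum over treatment intervals of (last dose − first dose + 1). For the Week 2 to Week 4 pattern this gives (13 − 0 + 1) + (83 − 28 + 1) = 14 + 56 = 70 days, as it should. If the first-to-last-dose figure is also wanted, show it on its own line and label it as a span.

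Two rules should stay as written. The second-interval last-dose date is the right anchor for the SAP 9.1 window, which requires that events start on or after first dose "and occur within 30 days of the last study drug dose". The cut in missed doses and compliance at first clearance is also sensible; a table footnote should say that those counts cover the first course only.

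The cost is one SAP sentence and one derivation change, with no protocol change. SAP 4 already relies on a second-interval last dose, and dosing diaries are collected at Weeks 4, 8 and 12. The documents do not show that the first course's last dose and the second course's first dose are held as database fields, so that should be confirmed. If they are not, the clearance and re-dispensing visit dates give an approximation.

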## 4.1. Sample Size

This study is not powered to detect a statistical difference in efficacy between treatment groups. Approximately 120 subjects will be randomized into the study in a 3:1 ratio (active:vehicle) at approximately 15 sites in North America. The number of subjects enrolled in any dosing cohort is dependent on the recommendations of the DSMB and enrollment rates. The main objective of this study is to evaluate the tolerability, safety, and efficacy of topical NVN1000 Gel.

#### 4.2. Randomization, Stratification, and Blinding

Subjects will be randomized to variable doses of NVN1000 or Vehicle Gel in a 3:1 ratio (active:vehicle) through utilization of the interactive voice response system/interactive web response system (IVRS/IWRS). The evaluator, Investigator, and subject will be blinded to the subject's treatment. NVN1000 Gel and Vehicle Gel are similar in appearance and cannot be differentiated.

In the event that a subject should experience an AE for which it is medically required to break the blind in order to determine appropriate treatment, unblinding can be achieved by using the IVRS/IWRS administrator. A study subject for whom the blind is broken

will discontinue study product and will be scheduled for a follow- up safety visit and be encouraged to stay in the study until the AE is resolved or stabilized. Although not required, the Investigator should contact PPD medical monitor prior to breaking the blind.

Randomization treatment assignment and actual treatment received will be presented in a by subject listing.

## 4.3. Analysis Populations

## 4.3.1. Intent-to-Treat Population

The ITT population will include all study subjects who were randomized and dispensed study medication.

## 4.3.2. Safety Population

The safety population will include all randomized subjects with documented use of study medication (at least one application) and at least one post-baseline safety assessment. The statement that a subject had no AEs constitutes a safety assessment.

## 4.3.3. Per-Protocol Population

The PP population will include subjects with no noteworthy study protocol deviations (i.e., any subject or investigator activity that could have possibly interfered with the therapeutic administration of the treatment or the precise evaluation of treatment efficacy) prior to initial clearance of baseline warts, or Week 12/early termination if the subject does not achieve complete clearance at any time during the study. The PP population will include subjects in the safety population who do not meet any of the following criteria:

- Violated inclusion/exclusion criteria which have a potential impact on efficacy
- Have taken any concomitant medications likely to impact efficacy
- Have missed more than one interim study visit that they would have been eligible to attend as their EGW/PAW had not completely resolved
- Have not been compliant with the dosing regimen (i.e., subjects must apply 80-120% of the expected applications of study medication during participation in the study)

All significant protocol deviations will be documented in the Significant Protocol Deviations Rules document. Each significant deviation will be assigned a rule number and indication (yes/no) if the deviation will result in subject exclusion from the PP population. Prior to breaking the blind, other additional criteria may be added to the list to accommodate for unforeseen events that occurred during the conduct of the trial that result in noteworthy study protocol deviations. A by subject listing will be presented including the reason subjects are not included in any analysis population.

## 4.4. Assessment Windows

## 4.4.1. Study Day

When study day is used for display or in comparisons the following algorithm will be used:

- study day = date of assessment date of first dose of study medication +1, if date of assessment ≥ first dose date.
- study day = date of assessment date of first dose of study medication, if date of assessment < first dose date.

Note that this definition differs from the protocol in that the date of first dose of study medication is Day 1. The day before the date of first dose of study medication is Day -1. Study day for analysis is defined as per SDTM definition which does not include a study day Day 0.

### 4.4.2. Visit Windows

By-visit analyses will be performed using the reported CRF visit. The one exception is the Week 12/ET visit. For safety endpoints that are not measured at every visit (e.g. lab values and vital signs), the Week 12/ET will be mapped to Week 12 but presented in tables/listings as Week 12/ET. For all other endpoints, for subjects who complete the study, the Week 12/ET visit will be mapped to "Week 12" and used in by visit analyses. For subjects who are early terminations, the Week 12/ET visit will be mapped to "ET" (early term and will not be included in the by visit analyses. The ET visit may be used for LOCF of missing data. The ET visit will be carried forward only to visits for which the ET visit occurred prior to on the last study day of the analysis visit window using the following windows:

Analysis Visit	Visit Window (Based on Study Day)
Week 2	Day 2 to Day 22
Week 4	Day 23 to Day 45
Week 8	Day 46 to Day 71
Week 12	Day 72 +

Table 1: Analysis	Visit	Windows
-------------------	-------	---------

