### 4.3 TOLERABILITY ASSESSMENTS

The Investigator will evaluate the subject's genital/perianal area prior to the first application of investigational product in addition to evaluating at each study visit. The tolerability assessment for visits other than Baseline should be performed at least 30 minutes after study drug application and prior to wart counts. Tolerability evaluations will include erythema, edema, erosions/ulceration and burning/stinging. Burning/stinging will be based on the subject's report

of local symptoms for the previous 24 hours. The highest severity of each parameter will be recorded. Tolerability endpoints will not be reported as an AE unless they reach severe and/or result in subject's discontinuation from the study. Tolerability assessments will be performed according to the following scales:

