### 6.7 DISCONTINUATION OF INDIVIDUAL SUBJECTS FROM THE STUDY

Subjects who develop intolerance to the product as defined by scores of 'severe' (3) on 2 or more categories of tolerability (erythema, edema, erosions/ulcers, burning/stinging) shall be discontinued from the study.

Subjects with a confirmed methemoglobin > 5.0% at any post-baseline visit will be discontinued from the study. A confirmed methemoglobin is defined as at least 2 readings within 0.5% of each other taken within a 30 minutes period.

If a subject is determined to be pregnant prior to Week 12, the subject will be discontinued from the study but followed until term.

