### 7.6 TOLERABILITY ANALYSIS

Tolerability assessments (erythema, edema, erosions/ulcerations, burning/stinging) will be summarized using frequency distributions at Baseline, Weeks 2, 4, 8, and 12/ET, as well as the worst post-baseline assessment. The number and proportion of subjects with a severe assessment or a two step severity increase from baseline will be summarized by treatment group at Weeks 2, 4, 8 and 12/ET for each assessment and for any assessment. In addition, shift tables will be presented.

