#### **Burning/Stinging**

Score	Description
0-None	No burning/stinging
1-Mild	Slight warm, burning/stinging sensation; not very bothersome
2-Moderate	Definite warm, burning/stinging sensation that is somewhat bothersome
3-Severe	Hot, tingling/sensation that has caused definite discomfort and may
	have disturbed sleep

Tolerability assessments (erythema, edema, erosions/ulcerations, burning/stinging) will be summarized using frequency distributions at baseline, Weeks 2, 4, 8, and 12/ early termination (ET), as well as the worst post-baseline assessment. The worst post-baseline assessment will be determined individually for each tolerability parameter. (e.g., the worst assessment for erythema may occur at a different visit than the worst assessment for edema.) The number and proportion of subjects with a severe assessment or a two step severity increase from baseline will be summarized by treatment group at Weeks 2, 4, 8, and 12/ET for each assessment and for any assessment. Vehicle Gel subjects will be separated into QD and BID groups. Additionally, the number and percentage of subjects who have 2 or more severe assessments at the same visit for any visit will be presented. A shift table will also be presented by tolerability parameter and treatment group, and all tolerability scores will be listed.

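### SAP 4.4.2 and SAP 8.3 give conflicting rules for early-termination tolerability scores in by-visit tables, and 4.4.2 wrongly classes vital signs as not taken at every visit (minor)

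*SAP*

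**What the plan says.** SAP 4.4.2 bases by-visit analyses on the visit recorded in the CRF, with one exception, the Week 12/ET visit. That exception has two branches.

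- **Branch A.** Safety endpoints not taken at every visit, with laboratory values and vital signs as the examples: the Week 12/ET visit is mapped to Week 12 and displayed as Week 12/ET, whenever it took place.
- **Branch B.** All other endpoints: completers' data go to Week 12, while an early terminator's data are mapped to ET ("early term and will not be included in the by visit analyses"). The ET value may be used for LOCF.

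For tolerability, Protocol 4.3 calls for evaluation "prior to the first application of investigational product in addition to evaluating at each study visit". Protocol 7.6 says the scores "will be summarized using frequency distributions at Baseline, Weeks 2, 4, 8, and 12/ET, as well as the worst post-baseline assessment". SAP 8.3 repeats that display and adds a subject count worded as follows: "severe assessment or a two step severity increase from baseline will be summarized by treatment group at Weeks 2, 4, 8, and 12/ET" (number and proportion).

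For vital signs, the schedules in both documents mark blood pressure and pulse at every visit, and Protocol 4.4.3 agrees. SAP 9.3 summarises change at Weeks 2, 4, 8 and 12 with no ET label. SAP 9.2 defends pooling ET with Week 12 on the ground that the tests are not done at each visit, and confines that argument to laboratory tests.

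**The concern.** Tolerability is a stated objective. Under Protocol 6.7, subjects scored severe "on 2 or more categories of tolerability (erythema, edema, erosions/ulcers, burning/stinging) shall be discontinued from the study", and Protocol 4.1.7 asks for the Week 12/ET evaluations at the time of premature discontinuation. An ET form can therefore carry the scores of someone who stopped because of intolerance. Read literally, SAP 4.4.2 keeps those scores out of the by-visit tolerability tables, while SAP 8.3 puts them in. Two programmers could build different tables from the same data, and interim Table 14.3-3.1 inherits the ambiguity.

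The severe-or-two-step summary is the most exposed display. It is specified by visit only; the worst-post-baseline row is attached to the frequency distributions, not to this summary. Under 4.4.2, an event seen only at ET would have no row in it.

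For vital signs the instruction is clear but its premise is wrong. The result is that an early reading is pooled with readings taken at the end of treatment.

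**Working it through.** **Step 1: which branch applies.** Visits carrying each assessment, from the Schedule of Events (Screening, Baseline, Weeks 2, 4, 8 and 12/ET):

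| Assessment | All 6 visits | 4 post-baseline visits | Branch by the 4.4.2 criterion |
|---|---|---|---|
| Blood pressure and pulse | 6 of 6 | 4 of 4 | B, but 4.4.2 names it under A |
| Tolerability | 5 of 6 (all from Baseline) | 4 of 4 | B, but 8.3 uses the A-style label |
| Methemoglobin | 4 of 6 | 2 of 4 | A |
| Chemistry, hematology, PT/PTT | 3 of 6 | 1 of 4 | A |

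Only the laboratory tests and methemoglobin fit branch A.

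**Step 2: the tolerability rows.** Take one subject who terminates early and whose only severe score is on the ET form. The contribution to the severe count is:

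| Rule | Week 2 | Week 4 | Week 8 | Week 12(ET) |
|---|---|---|---|---|
| SAP 4.4.2, branch B | 0 | 0 | 0 | 0 |
| SAP 8.3 and Protocol 7.6 | 0 | 0 | 0 | 1 |

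The result is the same whether the ET visit falls on Day 10, 30 or 60, because neither rule uses the day for this purpose. LOCF does not close the gap: it is specified for the efficacy endpoints in SAP 8.2.3 to 8.2.7 and not in 8.3.

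**Step 3: the vital-signs pooling.** Assume the first dose is on the Baseline date. SAP 4.4.1 makes that date Day 1, so a visit d days after Baseline is study day d + 1. As a check, the latest Week 2 visit is 14 + 3 + 1 = Day 18, the day SAP 8.2.8 uses. The Week 12 window is 84 − 5 + 1 = Day 80 to 84 + 5 + 1 = Day 90. A blood pressure taken at an ET visit on Day 10 is then pooled with readings scheduled 80 − 10 = 70 to 90 − 10 = 80 days later. SAP 4.4.2 would show the row as Week 12/ET; SAP 9.3 calls it Week 12.

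**Step 4: where ET tolerability scores remain.**

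- The worst-post-baseline frequencies (SAP 8.3, Protocol 7.6).
- The any-visit count in SAP 8.3: "the number and percentage of subjects who have 2 or more severe assessments at the same visit for any visit will be presented".
- The listings.
- Possibly the shift table, whose time points are not stated.
- AE records, for severe or discontinuing reactions. Protocol 4.3: "Tolerability endpoints will not be reported as an AE unless they reach severe and/or result in" discontinuation. SAP 9.1 lists the onset day.

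The case with least cover is a rise from 0 to 2 on the ET form of a subject who leaves for another reason. It is not an AE. It counts as a 2 in the worst-post-baseline frequencies, but under 4.4.2 only the shift table, if it includes ET, would tabulate it as a two-step increase.

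**The case against.** The strongest reply is that the tolerability conflict largely resolves on reading. SAP 4.4.2 says endpoints whose ET data are kept will carry the Week 12/ET label. SAP 8.3 uses that label for tolerability, 9.2 uses it for laboratory tests, and the efficacy sections use plain week numbers. SAP 4 places tolerability among the safety analyses. Protocol 7.6 agrees with 8.3, so two specific sections stand against one general paragraph. A literal reader could also say that tolerability, not being scored at Screening, is not taken at every visit and so belongs in branch A.

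Most of this stands: 12/ET is the better-supported reading. But no text makes 8.3 an exception, 4.4.2 is categorical, and the Screening argument sits badly with Protocol 4.3 and with a rule about post-baseline tables. The point is therefore an unreconciled rule, not a settled exclusion.

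For vital signs, the reply is that 4.4.2 names them, so the programmer knows what to do; all values are listed, and clinically significant changes become AEs. That too is fair. What remains is a false premise, an early reading pooled with Week 12, and a row label in 9.3 that does not match.

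A reader might also argue that an ET score ought to appear in the week in which it was taken, using the windows in SAP Table 1. The SAP does not say so. By-visit analyses follow the CRF visit, and Table 1 only limits how far an ET value may be carried forward. Windowing is a preference and not a standard the plan has broken.

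**Conclusion.** The point holds as a minor inconsistency. SAP 4.4.2, taken literally, removes ET tolerability scores from by-visit tables that SAP 8.3 and Protocol 7.6 say include them, and it misclassifies vital signs. The size is one row entry per affected subject (0 or 1 in the 12/ET row), together with early vital signs pooled with Week 12. The 70-to-80-day figure rests on the first dose being on the Baseline date and on an illustrative Day 10 ET visit.

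Three stronger inferences are not supported.

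- *That intolerance data are lost.* They remain in the displays listed in Step 4 of the working.
- *That DSMB or efficacy conclusions are affected.* The tables are descriptive, SAP 10 leaves the DSMB outputs to the charter, and no efficacy endpoint or test is involved.
- *That a distorted severe rate can be calculated.* Protocol 1.5 reports two Cohort 1 subjects with severe reactions leading to treatment discontinuation, but does not say on which visit form the scores were recorded or which treatment they received. Cohort sizes are not fixed, so no table-level rate follows.

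**What to change.** 1. **Tolerability.** State in SAP 4.4.2 that tolerability is an exception: ET scores are included in the 12/ET row of SAP 8.3 and Protocol 7.6, with the number of subjects assessed as the denominator. In 8.3, add a worst-post-baseline row to the severe-or-two-step summary, so that an ET event is counted whatever its timing. Use the same derivation for interim Table 14.3-3.1.
2. **Vital signs.** Remove vital signs from the example in 4.4.2, so that early ET readings are no longer pooled with Week 12. List those readings or show them in a separate ET row, and word SAP 9.3 to match.

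Assigning ET values to the Table 1 windows is optional. It would depart from the CRF-visit rule and would need new rules for ties and for Day 1, which precedes the first window (Day 2 to Day 22).

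The cost is a few sentences of SAP wording and a small programming change. No new data are needed, and the 12/ET row of Protocol 7.6 is kept.
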